3.2 Analysis datasets

Describe the datasets that will be used in the analysis, like the examples below.

- Intent-to treat (ITT) population: The ITT population will consist of all randomized participants in the groups to which they were randomly assigned.
- **Modified Intent-to Treat (MITT):** All participants in ITT population who have partial outcomes (i.e. data available for V2 or V3).
- **Per-Protocol (PP) population**: The PP population will consist of all participants who fulfil the protocol in the terms of eligibility, interventions, and outcome assessment without any major protocol deviation.
- **Per-Protocol Modified (PPM) population:** All participants in the PP population who were identified to be subjected to the protocol deviation documented in 173/CNBS/23.

4 Description of statistical methods

4.1 General approach

All analyses will be performed on the MITT and PP populations. Because there was a protocol deviation (i.e. participants with missing V2 or V3), the potential difference in the primary outcome between the two populations will be explored as described in *Section 7.0*.

All analyses (i.e. generalized linear models and proportional hazards models) will take into account the effect of the clusters using a mixed model approach, introducing a random intercept for each cluster. Details of the models for each outcome are given in the sections below.

For all statistical tests, alpha will be set to 0.05 for rejecting the null hypothesis. Since multiple comparisons will be performed, p-values will be adjusted using Benjamini-Hochberg method.

The proportion of observations with missing values will be summarised for all outcome variables. Missing and invalid data will not be imputed. Baseline measures will be reported for individuals with missing data on an outcome of interest, including those who withdraw or are lost to follow-up. For each analysis, the baseline measures (demographic and laboratory data) will be compared between participants with complete and incomplete data using T-Tests or Chi² tests, for continuous or categorical variables respectively.

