A cluster randomized controlled trial to evaluate the effect of placing Truenat platform/TB assays at primary health care clinics combined with rapid communication of results on time to treatment initiation of microbiologically confirmed TB. In a setup period (survey of study centers) before randomization, the healthcare facilities (=clinics) of 4 sites will be asked to provide information about the number of TB notifications per quarter covering the period 1/2018-6/2020. From this information the foreseeable number of examined patients ("size of a clinic") will be derived, which will be used as a strata variable in randomization process.

Facilities will be randomly allocated to the standard of care (control), or Truenat platform/TB assays. A cluster refers to a

	EDCTP
	clinic. The clusters will be assigned to intervention or control arm to one of two diagnostic procedures (SOC [smear microscopy and/or Xpert MTB/RIF Ultra off-site] vs Truenat platform/TB assays on-site) following a restricted randomization strategy, whereby 6 to 8 strata of clusters will be established using the stratification variables site (clinics belong to a site) and size and apply balance criteria for them. The number of strata per site depends on heterogeneity of the sizes of the clinics as established in setup period and may be increased, typically 1 or 2 strata per site will be established. The primary endpoint will be compared in an individual level analysis with strata and intervention as fixed effects and cluster as random effect.
Population	A total of 29 clinics will be randomized at the four participating sites aiming to enrol up to 150 adults (≥ 18 years of age) each (total approximately 4200) with signs and symptoms suggestive of TB. The number of clinics might be extended up to 37 due to the information gained in the setup period. Dependent on the loss to follow-up at 7 days, recruitment may need to be extended.
Inclusion/Exclusion Criteria (Site)	Based on information gained in the setup period sites will be included in the randomization process using the following criteria: Inclusion Criteria: Provision of TB treatment at the clinic Availability of electricity Willingness to participate Exclusion criteria: Patients with TB referred for treatment to other sites Sites with less than 10 patients registered for TB treatment per quarter

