9.6.1 Primary endpoint

The primary endpoint is the estimate of the number and proportion of participants with microbiological confirmation starting TB treatment within 7 days of their first visit among enrolled participants.

Protocol Version: 4.0 - CONFIDENTIAL - Page 32 of 57

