13. STATISTICAL CONSIDERATIONS

13.1 Populations to be analyzed

Intent-to treat (ITT) population: The ITT population will consist of all enrolled patients in the groups to which randomly assigned to intervention and controls. Patients with missing outcome data at days 7 and 60 will be assumed to not have started treatment.

Per-Protocol (PP) population: The PP population will consist of all patients who fulfil the protocol in the terms of eligibility, interventions, and outcome assessment without any major protocol deviation.

The Statistical Analysis Plan (SAP) will define the criteria for the exclusion of patients from any of the above-mentioned analysis populations and will be finalized prior to database lock. The SAP will also provide a detailed summary of the analysis methodology for each of the outcomes of the trial.

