13.8 Sample size determination

For the purpose of sample size estimation, a matched design is regarded which is known to have a similar power in the range of number of clusters per treatment arm similar to this study (~15, 30). Sample size calculation were based on 972 scenarios using assumptions for

- TB prevalence: 12%, 16%, 20%
- Sensitivity for intervention group: 89%
- Sensitivity for control group: 70%, 75%, 80%
- Diagnostic LTFU intervention arm: 2%
- Diagnostic LTFU control arm: 5%, 10%
- Pre-treatment LTFU¹ intervention arm: 8%, 10%, 12%
- Pre-treatment LTFU control arm: 16%, 20%, 24%³¹
- Cluster size CS 100, 125, 150, 200 (cluster sizes are regarded as average values of a distribution of cluster sizes).
- Within pair coefficient variation \mathcal{CV}_m : 0.25 according to recommendation in case of missing information given in
- Alpha-level α = 0.05
- Power: 80% (β = 0.2)

From the prevalence, sensitivity and LTFUs in the diagnostics the proportions p of treated patients is derived ($p = prev \cdot sens \cdot (1 - LTFU_{diag}) \cdot (1 - LTFU_{pre - ther})$ for each of intervention and control arm ($\rightarrow p_i, p_c$).

The number of cluster pairs N_{cp} is calculated according to the following formula [Hayes RJ, Moulton LH 2017]:

$$N_{cp} = A + \left(z_{\alpha/2} + z_{\beta}\right)^{2} \frac{p_{i}(1 - p_{i})/CS + p_{c}(1 - p_{c})/CS + CV_{m}^{2}({p_{i}}^{2} + {p_{c}}^{2})}{(p_{i} - p_{c})^{2}}$$

whereby the result is rounded up to the next whole number, with A = 1 [Hayes RJ, Moulton 2017]²⁹. Note that Software PASS [PASS 2020] uses A=2, [Hayes and Bennett 1999]³⁰ uses A=0. z = quantile of normal distribution.

col Version: 4.0 - CONFIDENTIAL - Page 44 of 57

One should note that smaller cluster sizes (which would result in more clusters) are advantageous in terms of total number of patients to be recruited. Thus, the scenario has to be selected taking in into account number of patients on the one hand and efforts to recruit and organise sites on the other hand.

Following scenarios have been selected according to feasibility and mid-range choice of the ranges presented above:

Cluster size		Prevalence	Sensitivity control	diagn. LTFU control (diagn. LTFU for intervention: 0.02)	pre-trt. LTFU intervention	pre-trt. LTFU control	success proportion intervention	success proportion control	number of cluster pairs	Number of clusters	Number of patients
	100	16%	70%	10%	10%	20%	13%	8%	14	28	2800
	100	12%	70%	10%	8%	20%	10%	6%	15	30	3000

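### The SAP models only participants with follow-up data (MITT) and PP, so the protocol's primary proportion (all enrolled, missing counted as not started) is never modelled

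*SAP*

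**What the plan says.** **Protocol.** Section 9.6.1 defines the primary endpoint as the number and proportion with microbiological confirmation "starting TB treatment within 7 days of their first visit among enrolled participants". Table 1 (Section 13.5) gives all participants as the denominator and lists the V2 call, the register and the study TB outcome worksheet as sources. Section 13.1 defines ITT as all enrolled patients by allocation and adds: "Patients with missing outcome data at days 7 and 60 will be assumed to not have started treatment".

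**SAP.** Section 3.2 keeps an ITT definition without the missing-outcome rule and adds MITT: "All participants in ITT population who have partial outcomes (i.e. data available for V2 or V3". Section 4.1 says "All analyses will be performed on the MITT and PP populations" and "Missing and invalid data will not be imputed". Sections 4.2 and 4.3, which specify the models, name no other population. ITT returns only in Section 5, among the sets to be described. The change history records that MITT was added in June 2023 and gives no reason.

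**The concern.** The protocol fixes a denominator and a rule for missing outcomes, and the SAP applies neither in any model. MITT and PP both depend on information that arises after enrolment, and Protocol 9.5.4 says clinicians and participants cannot be blinded. If the chance of having follow-up data differs by arm, the comparison is no longer the one that randomisation protects.

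There is also an ambiguity about who is in MITT. The SAP does not say whether register or worksheet data count as V2 or V3 data. If only interviews count, a participant who was never reached, but whose treatment start is in the register or TB outcome worksheet (Protocol 9.8), leaves the model. That would remove a documented success and so affect the count as well as the proportion. SAP 7 says that where V2 was not done, V3 was not done either, so under the interview reading a missed V2 is enough for exclusion.

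**Working it through.** **Step 1: the passages side by side.**

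| | Protocol 9.6.1, Table 1, 13.1 | SAP 3.2, 4.1 |
|---|---|---|
| Denominator | all enrolled | V2 or V3 data available (MITT), or PP |
| Missing outcome | counted as not started | not imputed |
| All-enrolled model | implied by the endpoint | none |

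**Step 2: reproduce the design figure.** Inputs from the final scenario in Protocol 13.8: prevalence 12%, sensitivity 89% and 70%, diagnostic loss 2% and 10%, pre-treatment loss 10% and 20%, cluster size 150, CV 0.25.

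- p_i = 0.12 × 0.89 × 0.98 × 0.90 = 0.0942
- p_c = 0.12 × 0.70 × 0.90 × 0.80 = 0.0605
- Difference 0.0337; OR = (0.0942/0.9058)/(0.0605/0.9395) = 1.62
- V = p_i(1−p_i)/150 + p_c(1−p_c)/150 + 0.0625(p_i² + p_c²) = 0.000569 + 0.000379 + 0.000783 = 0.001731
- Pairs = 1 + 7.849 × 0.001731/0.0337² = 12.95, rounded up to 13, as stated
- Power at 14 pairs (A = 1) = Φ(√(13 × 0.0337²/0.001731) − 1.96) = Φ(0.962) = 83.2%

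**Step 3: what dropping unreached participants could do.** The documents give no unreached rate by arm, so every loss rate here is an assumption. Assume that everyone dropped did not start treatment and that the all-enrolled rates equal the design values. With a share u of an arm dropped, the MITT rate is p/(1−u) and the cluster size is 150(1−u).

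| Assumed loss, intervention/control | MITT rates | OR | Power |
|---|---|---|---|
| none | 9.42% v 6.05% | 1.62 | 83.2% |
| 10%/10% | 10.47% v 6.72% | 1.62 | 83.4% |
| 5%/10% | 9.92% v 6.72% | 1.53 | 73.4% |
| 10%/5% | 10.47% v 6.37% | 1.72 | 90.4% |

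These are simple two-proportion ORs, not outputs of the adjusted mixed model.

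**Step 4: the count.** With 14 × 150 = 2100 per arm, the design expects 2100 × 0.0942 = 198 starters v 2100 × 0.0605 = 127. In Step 3 only non-starters leave, so these counts do not change; only the denominators shrink (to 1995 v 1890 at 5%/10%). The count changes only if MITT drops people with a documented start. As an assumed example, if 5% of intervention starters and 10% of control starters were dropped, the counts become 198 × 0.95 = 188 and 127 × 0.90 = 114, and their ratio moves from 1.56 to 1.56 × 0.95/0.90 = 1.64.

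**The case against.** **The protocol never names ITT as the primary analysis set.** That is true. The conclusion is inferred from the endpoint's denominator and the missing-data rule, which agree with each other.

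**Protocol 13.1 lets the SAP define exclusion criteria.** It does so for the populations it names, ITT and PP. One may argue that MITT is ITT with such a criterion. The clause still does not cancel the denominator in 9.6.1 or the rule stated in the same section.

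**MITT may be nearly everyone.** Protocol 9.8 provides three contact attempts, a proxy and up to three home visits in both arms, and registers are checked weekly. SAP 7 says retrospectively entered data were cross-checked against treatment registries. If register data count, few may be excluded. This stands as a real possibility, but the SAP does not say so.

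**SAP 5 covers outcomes in ITT, and SAP 4.4 examines missingness.** Both are true. Section 5 offers summaries and simple two-group tests that take no account of clustering, and Section 4.4 commits to no all-enrolled model.

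**Stronger readings that the documents do not support.**

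- A reader might infer from "From the prevalence, sensitivity and LTFUs in the diagnostics the proportions p of treated patients is derived" that the trial was powered for a missing-equals-failure analysis, or might use the 2% v 10% diagnostic losses as non-contact rates (giving OR 1.48 and power of about 66%). Those terms multiply prevalence and sensitivity, so they are care-cascade losses among TB cases. A patient lost from the cascade can still be reached at V2 and stay in MITT as a failure.
- A reader might take the synopsis sentence "Dependent on the loss to follow-up at 7 days, recruitment may need to be extended" as a forecast of heavy loss. It is conditional and gives no rate.
- A reader might treat the 808 participants in SAP 7 as missing outcomes. That section describes them as contacted outside the window.

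**Conclusion.** The concern holds: the all-enrolled proportion with missing counted as not started, which the protocol defines, is not estimated by any model in the SAP. This rests on the text alone.

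The numerical consequence cannot be determined from the documents. Equal loss is nearly harmless to the OR. Modest unequal loss of non-starters could move it from 1.62 to about 1.53 or 1.72, depending on which arm loses more. These figures assume design-value rates, assumed loss rates and no hidden starts among those dropped; under those conditions the count of starters is unaffected. A claim that MITT favours one arm, or that the design's power is lost, goes beyond the documents.

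**What to change.** Before database lock, amend SAP 3.2 and 4.1 as follows:

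- Make all enrolled participants, by clinic allocation, the primary set for both the proportion and the count model.
- Take the day-7 outcome from the register and TB outcome worksheet plus V2, and count no evidence of a start as not started, as in Protocol 13.1.
- Keep MITT and PP as sensitivity analyses, and state that register and worksheet data count as outcome data for MITT.

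A tipping-point table by arm, for participants with no evidence from any source, is a cheap optional addition, since starts at other providers may come to light only through contact.

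As a separate, smaller point, reconcile the description of the protocol deviation. SAP 3.2 places the affected participants (PPM) inside PP, while SAP 7, item 5, describes PP as those without the deviation. SAP 4.1 calls the deviation missing visits, while SAP 7 calls it out-of-window contact. Until this is settled, membership of PP is unclear.

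The cost is SAP wording, one extra model run per primary comparison and, if wanted, one table. No new data or participants are needed.

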	100	12%	70%	10%	10%	20%	9%	6%	17	34	3400
	100	12%	70%	10%	12%	20%	9%	6%	18	36	3600
	150	12%	70%	10%	10%	20%	9%	6%	13	26	3900
	150	16%	70%	5%	10%	20%	13%	9%	14	28	4200
	150	16%	70%	10%	10%	20%	13%	8%	12	24	3600
	200	12%	70%	10%	10%	20%	9%	6%	12	24	4800
	200	16%	70%	5%	10%	20%	13%	9%	13	26	5200
	200	16%	75%	10%	10%	20%	13%	9%	14	28	5600

Table 2: selected scenarios. Colours vary with cluster size and prevalence. Red: final scenario.

Applying an alpha-level of 0.05, a power of 80%, 12% prevalence, diagnostic LTFU-rates of 10% (control), 10% (pre-treatment intervention), 20% (pre-treatment control), a cluster size of 150 and a within-pair coefficient of variation (default value 0.25²⁹), the results bring a total of 13 cluster pairs (3900 patients). In order to address uncertainty, 1 additional cluster pair will be added, bringing the total to 14 cluster-pairs (28 clinics, 4200 patients) to be included in the trial. If based on what will be observed in the initial setup period, smaller than average cluster sizes are expected, more sites will need to be included in the trial in order to match the total sample size.

Protocol Version: 4.0 - CONFIDENTIAL - Page 45 of 57

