2.1 Primary endpoint

The primary outcome of the study is the absolute number and point estimate (with 95% CIs) of the proportion of participants with TB microbiological confirmation starting TB treatment within 7 days of their first visit. We evaluate the probability of the patients in the intervention arm (with Truenat) for a favourable outcome of interest compared to patients in the SOC arm as a binary outcome of success or failure.

The hypotheses of interest are:

and,

 ${\it H0}:$ Number of successes in intervention arm is same as in the SOC arm.

H1: Number of successes in intervention arm is different from the SOC arm

H0: Proportion of success in intervention arm is same as in the SOC arm.

H1: Proportion of success in intervention arm is different from the SOC arm

This is translated in terms of odds ratio (OR) for odds of success in the intervention arm to be different from the odds of success in the SOC arm thus leading to the definition of the following hypothesis:

QMS Form number: FM-06-02-	CONFIDENTIAL	Page 6 of 26
05/v2.0		-

FIND >>>	Statistical Analysis Plan		
Protocol number:	TB041-3/1-TAN / -MOZ		
Document version:	5.0	Document date:	11-JUL-2023

 $H0: OR_{Intervention:SOC} = 1 \text{ vs. } H1: OR_{Intervention:SOC} \neq 1$

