- 5) A survival analysis will be performed on PP (i.e. participants without the protocol deviation) and in PPM population on time to treatment initiation to explore the possibility of bias.

Other measures can be taken depending on the distribution of the outcome related data

8 Sample size

For the purpose of sample size estimation, a matched design is considered which is known to have a similar power in the range of number of clusters per treatment arm similar to this study (~15). Sample size calculations were based on 972 scenarios using the following ranges of assumptions:

- TB prevalence: 12%, 16%, 20%
- Sensitivity for intervention group: 89%
- Sensitivity for control group: 70%, 75%, 80%
- Diagnostic LTFU intervention arm: 2%
- Diagnostic LTFU control arm: 5%, 10%

QMS Form number: FM-06-02-	CONFIDENTIAL	Page 19 of 26
05/v2.0		-

FIND >>>	Statistical Analysis Plan			
Protocol number:	TB041-3/1-TAN / -MOZ			
Document version:	5.0	Document date:	11-JUL-2023	

- Pre-treatment LTFU intervention arm: 8%, 10%, 12%
- Pre-treatment LTFU control arm: 16%, 20%, 24%¹
- Cluster size CS 100, 125, 150, 200 (cluster sizes are regarded as average values of a distribution of cluster sizes).
- Within pair coefficient variation CV_m: 0.25 according recommendation in case of missing information given in³²
- Alpha-level $\alpha = 0.05$
- Power: 80% ($\beta = 0.2$)

From the prevalence, sensitivity and LTFUs in the diagnostics the proportions p of treated patients is derived ($p = prev \cdot sens \cdot (1 - LTFU_{diag}) \cdot (1 - LTFU_{pre-ther})$ for each of intervention and control arm ($\rightarrow p_i, p_c$).

The number of cluster pairs N_{cp} is calculated according to the following formula [Hayes RJ, Moulton LH 2017]:

$$N_{cp} = A + (z_{\alpha/2} + z_{\beta})^{2} \frac{p_{i}(1 - p_{i})/CS + p_{c}(1 - p_{c})/CS + CV_{m}^{2}(p_{i}^{2} + p_{c}^{2})}{(p_{i} - p_{c})^{2}}$$

whereby the result is rounded up to the next whole number, with A=2, z= quantile of normal distribution.

The following scenarios have been selected according to feasibility and mid-range choice of the ranges presented above are shown in the tabulation below. Colours vary with cluster size and prevalence. The finally selected scenario is described below in red.

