Cluster size	Prevalence	Sensitivity control	diagn. LTFU control (diagn. LTFU for intervention: 0.02)		pre-trt. LTFU control	success proportion intervention	success proportion control	number of cluster pairs	Number of clusters	Number of patients
100	16%	70%	10%	10%	20%	13%	8%	14	28	2800
100	12%	70%	10%	8%	20%	10%	6%	15	30	3000
100	12%	70%	10%	10%	20%	9%	6%	17	34	3400
100	12%	70%	10%	12%	20%	9%	6%	18	36	3600
150	12%	70%	10%	10%	20%	9%	6%	13	26	3900

QMS Form number: FM-06-02-	CONFIDENTIAL	Page 20 of 26
05/v2.0		

FIND >>>	Statistical Analysis Plan				
Protocol number:	TB041-3/1-TAN / -MOZ				
Document version:	5.0	Document date:	11-JUL-2023		

150	16%	70%	5%	10%	20%	13%	9%	14	28	4200
150	16%	70%	10%	10%	20%	13%	8%	12	24	3600
200	12%	70%	10%	10%	20%	9%	6%	12	24	4800
200	16%	70%	5%	10%	20%	13%	9%	13	26	5200
200	16%	75%	10%	10%	20%	13%	9%	14	28	5600

Applying an alpha-level of 0.05, a power of 80%, 12% prevalence, diagnostic LTFU-rates of 10% (control), 10% (pre-treatment intervention), 20% (pre-treatment control), a cluster size of 150 and a within-pair coefficient of variation (default value 0.25), the results bring a total of 13 cluster pairs (3900 patients). In order to address uncertainty, 1 additional cluster pair will be added, bringing the total to 14 cluster-pairs (28 clinics, 4200 patients) to be included in the trial. If based on what will be observed in the initial setup period, smaller than average cluster sizes are expected, more sites will need to be included in the trial in order to match the total sample size.

Randomisation process

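### SAP 4.1 applies Benjamini-Hochberg without defining the family or exempting the primary endpoint, although the sample size assumes one unadjusted two-sided test at 0.05

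*SAP*

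**What the plan says.** SAP 4.1 sets the significance level in one sentence, "For all statistical tests, alpha will be set to 0.05 for rejecting the null hypothesis", and the multiplicity rule in the next, "Since multiple comparisons will be performed, p-values will be adjusted using Benjamini-Hochberg method". Both stand under the general approach. Neither there nor in SAP 4.2, which describes the primary analysis, is there a list of tests in the family, a count of them, or an exemption for the primary endpoint. SAP 4.3 analyses the binary secondary endpoints with the same models as the primary.

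The primary hypothesis is two-sided: the alternative is "Proportion of success in intervention arm is different from the SOC arm". SAP 2.1 also states a second null hypothesis for the number of successes, and SAP 4.2 gives it its own Poisson model.

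The sample size carries no multiplicity term. Protocol 13.8 begins its final scenario with "Applying an alpha-level of 0.05, a power of 80%, 12% prevalence", and SAP 8 repeats it. The result is 13 cluster pairs, raised to 14 (28 clinics, 4200 patients).

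**The concern.** A Benjamini-Hochberg adjusted p-value is never smaller than the raw one. Placing the primary in a large family therefore cannot help it and will usually hurt it. Whether the primary counts as significant would then depend on how many secondary tests succeed.

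Two things are at stake:

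- **Power.** The trial is justified by 80% power at an unadjusted 0.05. A pooled family would apply a stricter threshold, and the sample size makes no allowance for that.
- **A clear verdict on the main result.** If the family is still undefined when results are seen, its membership can be argued afterwards. SAP 4.2 also gives Wald 95% confidence intervals with no stated adjustment. The interval for the odds ratio could exclude 1 while the adjusted p-value exceeds 0.05.

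**Working it through.** **1. Reproduce the sample size.** Inputs from Protocol 13.8 and SAP 8: prevalence 12%; sensitivity 89% (intervention) and 70% (control, selected scenario); diagnostic loss to follow-up 2% in the intervention arm; then "diagnostic LTFU-rates of 10% (control), 10% (pre-treatment intervention), 20% (pre-treatment control), a cluster size of 150"; within-pair coefficient of variation 0.25.

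- p_i = 0.12 × 0.89 × 0.98 × 0.90 = 0.0942
- p_c = 0.12 × 0.70 × 0.90 × 0.80 = 0.0605
- N = A + (z_{α/2} + z_β)² × C, where C = [p_i(1−p_i)/150 + p_c(1−p_c)/150 + 0.25²(p_i² + p_c²)] / (p_i − p_c)²
- C = (0.000569 + 0.000379 + 0.000783) / 0.001137 = 1.522
- (1.960 + 0.842)² × 1.522 = 11.95

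With A = 1 (Protocol 13.8) this gives 12.95, so 13 pairs, as stated; all ten table rows reproduce. With A = 2 (printed in SAP 8) it gives 13.95, so 14 pairs, and no row reproduces. Both values are carried below.

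**2. Unadjusted power.** Power = Φ(√((N − A)/C) − 1.960).

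- 13 pairs, A = 1: √(12/1.522) = 2.807, power 80.2%
- 14 pairs, A = 1: √(13/1.522) = 2.922, power 83.2%
- 14 pairs, A = 2: √(12/1.522) = 2.807, power 80.2%

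**3. Count the tests.** SAP 2.2 yields: time to confirmation 1; treated with microbiological or clinical diagnosis 4; confirmed start by day 60, 2; start without confirmation at days 7 and 60, 4; start regardless of confirmation at days 7 and 60, 4; time to treatment 2; ongoing treatment 3 (proportions only, since the counts are excluded from formal testing); symptoms 3 (one test each); cost and productivity 3. The total is 26. Adding the primary proportion gives m = 27, and adding the primary count as well gives 28. If each number/proportion pair is one test, the total is 20. If the MITT and PP results both enter, it is 56, before the subgroup analyses in SAP 6.

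**4. Threshold for the primary in a family of 27.** If k other tests are rejected, the primary needs p ≤ 0.05(k + 1)/27.

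| Others rejected, k | Threshold | Power, 14 pairs, A = 1 | Power, 14 pairs, A = 2 |
|---|---|---|---|
| 0 | 0.00185 | 42.4% | 38.0% |
| 1 | 0.0037 | 50.8% | 46.2% |
| 6 | 0.0130 | 66.9% | 62.7% |
| 13 | 0.0259 | 75.6% | 71.9% |
| 20 | 0.0389 | 80.4% | 77.1% |
| 26 | 0.05 | 83.2% | 80.2% |

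For k = 0 and A = 1: Φ(2.922 − 3.113) = Φ(−0.191) = 0.424. For other family sizes, the same worst case with A = 1 is 46% (m = 20), 42.0% (m = 28) and 34.5% (m = 56).

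**5. Allow for the number of rejections being random.** Benjamini-Hochberg was simulated (100,000 runs, m = 27, 14 pairs), with each real secondary effect assumed as strong as the primary and correlation between tests of 0 or 0.5.

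| Real effects among the 26 others | Power, A = 1 | Power, A = 2 |
|---|---|---|
| 0 | 43% | 38–39% |
| 5 | 58–60% | 53–54% |
| 13 | 69–72% | 64–67% |
| 20 | 74–78% | 70–73% |
| 26 | 78–81% | 74–77% |

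**6. A single example.** A primary p-value of 0.03 in a family of 27 needs rank 0.03 × 27/0.05 = 16.2, so 17. At least 16 other tests would have to be rejected with it.

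**The case against.** A reader might infer that the SAP places every p-value in one family and that the 80% power is therefore lost. The documents do not support that as a statement of fact. The words about all statistical tests belong to the sentence on alpha, and the Benjamini-Hochberg sentence names no family. A secondary-only family would fit the unadjusted sample size. What stands against this defence is that neither document limits the rule to secondary endpoints, and its place under the general approach makes pooling the natural reading.

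A reader might also take the worst case as the expected loss, or say that unrelated endpoints would decide the primary result. Neither follows. The primary event, confirmed treatment start by day 7, is contained in confirmed start by day 60 (2 tests) and in any start by days 7 and 60 (4 tests), and it feeds both time-to-treatment analyses (2 tests). If the primary effect is real, at least some of these 8 are likely to be real too, although effects measured at day 60 may be smaller. A real primary effect with no other rejection is therefore improbable.

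Three further points are fair:

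- The 80% belongs to 13 pairs. The added pair raises the unadjusted power to 83% if A = 1.
- It is unclear whether the three cost and productivity tests enter the family. SAP 1.2 assigns them to a separate institution, and SAP 4.3 describes several such endpoints as not estimated by standard statistical analysis.
- The adjustment cannot raise the false-positive risk of the primary, and it leaves the estimated odds ratio unchanged.

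These points limit the size of the loss. They do not supply the missing definition.

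**Conclusion.** The concern holds in conditional form. The SAP leaves the Benjamini-Hochberg family undefined and does not exempt the primary, while the sample size assumes one unadjusted two-sided test at 0.05. If the primary proportion is pooled with the 26 secondary tests, its power at 14 pairs lies between about 42% and 83% with A = 1, or 38% and 80% with A = 2. With 5 to 13 real secondary effects of similar strength it would be roughly 58–72% (A = 1) or 53–67% (A = 2). It stays close to the unadjusted value only if nearly all the other tests are rejected as well.

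These figures rest on the plan's own design inputs, 14 pairs of average size 150, and a family of 27. The number, strength and correlation of the secondary effects are assumptions, so the result is a range and not a single figure. The extent of overlap with the primary makes a loss smaller than the worst case likely.

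**What to change.** Before results are seen:

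- **SAP 4.1:** state that the primary comparison of proportions, on which the sample size rests, is tested at two-sided 0.05 outside the Benjamini-Hochberg family. Apply Benjamini-Hochberg only to a listed family of secondary endpoints. The list should say which analysis set supplies the p-values and whether the cost and productivity tests are included.
- **SAP 2.1 and 4.2:** report the count comparison as supportive, so that it is not a second primary test. The protocol also defines the primary endpoint as a number and a proportion (synopsis, 9.6.1, Table 1), so a matching clarification there is probably needed.

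The cost is a few sentences, with no new data and no change to trial conduct. The statistical downside is that false discovery control no longer covers primary and secondary tests jointly. The type I error of the primary test remains 0.05.
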